**Table 1**

Data Class	Examples include, but are not limited to:	Data source
Clinician characteristics	sex, age, degree (MD, DO, NP, PA, resident), years of practice	Public faculty data

Encounter information	Encounter date, encounter type, clinician ID, reason for visit, level of service, clinic ID, Department ID, encounter ICD9/10 problems, encounter CPT codes, encounter payor(s), skin cancer screening performed, use of skin cancer screening tool, use of SKLIP , biopsy performed, referral to dermatology, econsult to dermatology. Use of skin cancer dot phrase, Established vs. new patient.  Patient characteristics age, sex, race, ethnicity.	EHR, chart review
biopsy info/ pathology	Biopsy result, number of biopsies performed, number of skin lesions biopsies, Breslow thickness	EHR, chart review
Clinician knowledge and confidence	MTED pre- and post-evaluations,	From IRB approved Surveys ( IRB #19372 – “Educational Program for the Early Detection of Melanoma in Oregon” ).
practice pattern, referral practice	qualitative Interviews	Coded qualitative interview transcripts

***Schedule of Events***

Procedures	Pre- Intervention		Intervention (~3 months)		Post-Intervention (~12 months)	
	Present	Apr 2023	Apr&May 2023	Aug – Oct 2023	Oct - Dec 2023	Jan - Sep 2024
Pre-intervention EHR Data pull		x				
Develop training materials		x				
Recruitment		x				
Initial Training			x			
Online Training			x	x	x	
Refresher trainings					x	
Intervention EHR Data pull			x			
Interview guide finalized				x	x	
Qualitative interviews				x	x	
Online survey (MTED) data pull				x	x	
Post- Intervention EHR Data pull					x	x
Data analysis					x	
Dissemination (manuscripts, results in clinicaltrials.gov, etc.)					x	x

**7) Data and Specimens**

**a. Handling of Data and Specimens**

The online surveys containing the knowledge assessments will be administered using Qualtrics, an OHSU approved survey application. The research faculty and staff who have access to the application for data management and analytic purposes are all trained in and comply with research ethics and policies related to research data confidentiality, privacy and security as part of their employment at OHSU. PCPs invited to complete the online training and knowledge assessments will generate a unique ID that will be requested each time a test is completed. Participants who request CME will need to provide names and email address but this data will not be linked to data collected in pre- and post-tests or unique ids.

Interviews will be transcribed and will not include interviewees' names during the interview and will be scrubbed during transcription process. If a third-party transcription service is used, we will go through OHSU approved vendor Landmark, for which we already have a contract in place. The audio files from interviews will be destroyed after the transcript is checked for accuracy.

All qualitative data (interviews and fieldnotes) will be stored in a password protected computer file on a secure workstation at OHSU and access is restricted to study personnel. Notes will not include identifying information about the clinic, health care providers, or patients. Access to data will be restricted and require OHSU ID/password authentication. Their study ID number will be used to be able to link the interview information with the EHR and clinician performance data.

No patients will be individually identifiable for analyses. Each patient will be assigned a unique identification number that is not based on any personal identifiers by the OHSU population health analysts (not part of the research team). OHSU data population health analysts will retain the crosswalk between identifiers and patient data, but not share it with the research team

For a subset of patients, we will obtain patients' medical records number (MRN) to conduct a chart review. The MRN will be linked to a patient's unique ID number in a separate document not for analysis. MRNs will not be recorded in any datasets used for analysis.

We will ensure proper protections are in place to securely transfer and store these data within OHSU to prevent disclosure. The limited data set will be analyzed by biostatisticians employed by the OHSU department of family medicine. All data will be stored on secure servers and password protected computers at OHSU. We have previous experience conducting these types of studies.

**b. Sharing of Results with Subjects**

Results of the study will not be shared with subjects. All findings will be reported in aggregate.

Meta data including codebook/data dictionary and a document describing data used in publications will be added to a repository for 10 years.

**8) Data Analysis**

Quantitative Data: Univariate descriptive statistics will be examined for all variables from the MTED pre- and post- evaluation survey. Comparison between data collection timepoints will be completed using Chi-square test (categorical), ANOVA (continuous), or Kruskal-Wallis one-way ANOVA test (continuous variables that are not normally distributed). Standard qualitative analysis techniques will be used for coding open-ended questions.

Descriptive statistics will be used to report screening, biopsy and referral characteristics at each data collection time points. Means, standard deviations will be reported for normally distributed continuous variables and medians and interquartile ranges (IQR) will be reported for non-

normally distributed ones. Frequencies and percentages will be calculated for categorical variables. The main comparison is between clinicians in the multicomponent educational intervention arm vs. clinicians at the same sites that do not have exposure to the multicomponent educational intervention. These two groups of clinicians are examined using a pre-post study design to evaluate outcomes including change in risk assessment, biopsy referral and identification of skin cancers. Linear mixed-effects regression models adjusting for clustering effects within study sites and other potential confounders will be used to compare the intervention and control arms in screening, biopsy and referral characteristics outcomes from baseline to post-intervention. A p-value < .05 will be considered statistically significant.

Qualitative data analysis: The study team will meet regularly to review fieldnotes and transcribed data and listen to and discuss key segments of the recorded interviews. Analyzing qualitative data as it is collected is crucial to monitoring data quality, refining interview guides, and monitoring theme saturation. This ongoing process will be used to track emerging themes and create a coding template to be used for more in-depth analysis. We will follow the 5-phase analysis strategy described by Miller and Crabtree (describing, organizing, connecting, corroborating/ legitimizing, representing). We will use an immersion-crystallization approach in which the team reads and discusses the data for each participant (immersion) to identify key findings (crystallization); first to identify key themes within each “case”, and then to identify cross-case findings.

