## 4) Study Design

This study is a mixed method pilot study to determine whether multicomponent education module improves the ability of Primary Care Providers (PCPs) to identify and triage skin cancer. The main independent variable is the multicomponent education for clinicians. This is primarily a feasibility study to evaluate the engagement and uptake of the training and change in skin cancer screening behavior on the part of clinical teams. We hypothesize that exposure to the intervention will increase clinician knowledge, increase the use of a SKLIP dermoscopy device to facilitate capture of high-resolution dermoscopy images, and increase screening for skin cancer.

Outcomes:

- Uptake of the training and performance of skin cancer screening processes measured by proportion of clinicians invited to participate in the educational intervention that complete the training modules; use of the Epic smart tool and dotphrases.
- Clinical knowledge measured through pre- and post-tests implemented during live (in-person or virtual) training.
- Use of the risk assessment tool measured through EHR data.
- Identification of suspicious lesions measured through EHR data.

We hypothesize that the multicomponent education strategy will result in the diagnosis of more skin cancers at earlier stages. Primary endpoints of the study include the pre- and post-intervention: number of melanomas biopsied, mean and median Breslow depth of melanomas biopsied, number of other malignant skin tumors biopsied, total number of referrals to dermatology, number of referrals to dermatology for concerning moles, and number of OHSU PCPs who access the Melanoma Toolkit for Early Detection (MTED), an online Continuing Medical Education training. There will be two comparison groups: OHSU PCPs receiving the intervention, OHSU PCPs not exposed to the intervention.

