The Melanoma Toolkit for Early Detection (MTED) is a Continuing Medical Education training that PCPs from the intervention arm of the study will be encouraged to complete as part of the intervention. Participants will be provided with a link by email to complete the training within the online platform. The Toolkit contains various Epic tools (SmartPhrases, the melanoma risk stratification framework, a skin cancer-specific after visit summary) and a self-paced online curriculum (see IRB #19372 – “Educational Program for the Early Detection of Melanoma in Oregon”). A separate copy of the online curriculum and surveys has been made specifically for this study to avoid cross-contamination of data. Knowledge will be assessed among the intervention participants as pre-post intervention evaluations. Knowledge and confidence assessments are embedded in the online learning MTED modules (as pre- and post-test surveys) and have demonstrated improvement in PCP melanoma knowledge and confidence in a prior study (Orfaly 2021). This information will allow us to measure the level of uptake of the curriculum and track any changes in overall referral and biopsy numbers of Toolkit-trained PCPs. The data will always be assessed as an aggregate and never on an individual provider basis. Individual PCPs will be de-identified and will create a unique ID. Those who complete the MTED training can request CME upon completion.

*Interviews:*

The study team will conduct interviews from the two study sites. We will invite everyone who participated in the first training to the interviews. Interview will last up to one hour and will take place outside of regular work hours.

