Enhancing Skin Cancer Early Detection and Treatment in Primary Care

NCT05675709

March 1, 2025

Final approach to analysis

Analyses

We used descriptive analyses to examine participating clinician characteristics and rates of e-consults, dermatology referrals and biopsies performed (defined as the number of cases per 1000 patients). We conducted a paired t-test to evaluate change in knowledge scores and used generalized estimating equation-based (GEE) models with link function of Poisson distribution and an exchangeable correlation structure to compare referral outcomes. The models included exposure to training (Yes/No), pre- and post-training time periods and the interaction of these two indicators as predictors. All analyses were two-sided, statistical significance was set at type I error of 5% and analyses were conducted using R Statistical Software.

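### Protocol section 8 prescribes independent-group tests for pre/post survey answers from the same clinicians; the SAP moves to a paired test for knowledge scores only and leaves confidence and any categorical items without a stated final method

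*Protocol*

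**What the plan says.** Protocol section 8 (Data Analysis, Quantitative Data) opens with descriptive statistics for "all variables from the MTED pre- and post- evaluation survey" and then gives the rule for testing change: "Comparison between data collection timepoints will be completed using Chi-square test (categorical), ANOVA (continuous), or Kruskal-Wallis one-way ANOVA test". It names no paired or repeated-measures version.

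Protocol section 6 (Online Training/Education) describes the data as repeated measurements: "Knowledge will be assessed among the intervention participants as pre-post intervention evaluations". It adds that confidence is measured in the same way: "Knowledge and confidence assessments are embedded in the online learning MTED modules (as pre- and post-test surveys". Table 1 lists clinician knowledge and confidence as a data class to be collected. Under section 7a, clinicians invited to the online training and knowledge assessments "will generate a unique ID that will be requested each time a test is completed".

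Protocol section 4 lists a knowledge outcome from a different occasion: "Clinical knowledge measured through pre- and post-tests implemented during live (in-person or virtual) training". Confidence is not in that outcome list.

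The SAP, titled "Final approach to analysis" and written in the past tense, has one sentence on survey data: "We conducted a paired t-test to evaluate change in knowledge scores". It mentions neither confidence nor categorical survey items.

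**The concern.** Pearson's chi-square, one-way ANOVA and Kruskal-Wallis all take their null variance from independent groups. Here each clinician contributes one answer before and one after training, and the two are likely to be positively correlated. An independent-group test then leaves the stable differences between clinicians in the error term, although pairing would remove them. The ANOVA standard error is too large, and the null variance behind chi-square and Kruskal-Wallis is too large for the same reason.

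What is at stake is lost sensitivity. In a pilot with about 40 trained clinicians, a real gain in confidence or in an item-level answer could be reported as non-significant because the linkage was not used. The two documents also differ on knowledge: section 8 covers every MTED variable with unpaired tests, while the SAP reports a paired one.

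**Working it through.** The documents give no effect size, standard deviation, pre-post correlation or power for the survey, so there is no planned figure to reproduce. What follows is an illustration.

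**Inputs**
- From the documents: two-sided 5% level (SAP); about 40 clinicians in the active intervention (Protocol section 5a), used here as 40 matched pairs.
- Assumed: equal SDs before and after; bivariate normal scores; correlation ρ of 0.3, 0.5 or 0.7; a shift of 0.4 SD for scores; for a binary item, a move from 40% to 60% with ρ as the latent correlation.

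**Standard error of the mean change, in SD units**
- Independent-group formula: √(2/n) = √(2/40) = 0.2236, whatever ρ is.
- Correct paired formula: √(2(1−ρ)/n) = 0.1871, 0.1581, 0.1225 at ρ = 0.3, 0.5, 0.7.
- Ratio 1/√(1−ρ) = 1.20, 1.41, 1.83.

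**Normal approximation**
- Type I error of the unpaired test = 2[1 − Φ(1.96/√(1−ρ))] = 1.9%, 0.6%, 0.04%.
- Power of the unpaired test = 1 − Φ((1.96 × 0.2236 − 0.4)/SE), with SE the paired value. The numerator is 0.4383 − 0.4 = 0.0383, so power is 42%, 40%, 38%.
- Power of the paired test = Φ(0.4/SE − 1.96) = 57%, 72%, 90%.

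**Simulation with t-tests, 40 pairs**

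| ρ | Unpaired type I error | Unpaired power | Paired power |
|---|---|---|---|
| 0.3 | about 2% | 41-42% | 55% |
| 0.5 | 0.7% | 39% | 69-70% |
| 0.7 | 0.05-0.1% | 37% | 89% |

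The paired test holds its level at about 5%. With two timepoints, one-way ANOVA is the two-sample t-test. Kruskal-Wallis behaves alike: simulated type I error is 2.3%, 0.7%, 0.1% at the same correlations.

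**Simulation for a binary item, 40% to 60%, 40 pairs (power)**

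| Latent ρ | Chi-square | McNemar, asymptotic | McNemar, exact |
|---|---|---|---|
| 0.3 | 46% | 51% | 42% |
| 0.5 | 44% | 56% | 47% |
| 0.7 | 44% | 67% | 57% |

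Repeated runs differ by about one percentage point. At latent correlation 0.3 the exact McNemar test has slightly less power than chi-square. The advantage of pairing for binary items is therefore modest unless the correlation is high or the asymptotic version is used.

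**Direction**
At ρ = 0 the two score analyses agree. The unpaired test becomes liberal only if ρ is negative (ANOVA type I error 7.4% at ρ = −0.2), which is not what one expects for the same person tested twice.

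**The case against.** A reader might infer that confidence and categorical items were in fact tested with unpaired methods. The documents do not show this. The SAP is the later, final statement and reports one survey test, a paired one. It does not say that the section 8 tests were kept for other items. Those items may have been dropped, only described, or tested. This objection stands.

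The listed survey outcome, clinical knowledge, already has a paired test in the SAP, and the change from section 8 is in the right direction. Confidence is collected but is not a listed outcome. That limits the reach of the point, although the SAP does not say which knowledge test its scores come from.

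The survey instruments are not in the documents, so it is not established that any categorical item is asked at both times. The harm at item level is conditional on such items existing.

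Forty matched pairs is probably optimistic. Forty is a recruitment figure, MTED is encouraged rather than required, and clinicians make up their own IDs. This also stands: with fewer pairs the power of either analysis is lower than shown.

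Finally, the word ANOVA could mean a repeated-measures ANOVA. Nothing in section 8 says so, its listed alternative is a one-way rank test, and that reading would still leave chi-square and Kruskal-Wallis unpaired.

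**Conclusion.** The rule in Protocol section 8 is wrong as written for pre/post survey comparisons, because it prescribes independent-group tests for linkable repeated measurements. The SAP replaces it for knowledge scores only. For confidence and any categorical items, the one method on record ignores pairing and the final method is unspecified.

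If the section 8 tests were used, the error would be conservative under positive correlation: effects missed, not false positives. For scores, the loss under the stated assumptions runs from roughly 14 percentage points of power (41% against 55%) to about 52 (37% against 89%). For binary items it is smaller, and with the exact test at low correlation there is none. The correlations, the shift and the number of pairs are assumptions; the fault in the rule does not depend on them.

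It would be too strong to read this as a threat to the study's main results. The biopsy and referral endpoints are analysed by other models and are untouched.

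**What to change.** In Protocol section 8, replace the chi-square/ANOVA/Kruskal-Wallis rule for pre/post survey comparisons with analyses paired by unique ID:
- paired t-test or Wilcoxon signed-rank for scores;
- McNemar for binary items, stating whether exact or asymptotic;
- a symmetry test for items with more than two categories.

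Report the number of matched pairs for each comparison.

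In the SAP:
- state whether confidence and categorical items were tested;
- if the section 8 tests were used, re-analyse those items as paired;
- say whether the knowledge scores come from the live-training test (Protocol section 4) or from MTED (section 6).

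The cost is a few sentences and, at most, a short re-analysis; no new data are needed. The downside is that records without a matching ID at both tests drop out of the paired comparisons. The documents give no rule for such records, so their number should be reported beside the matched pairs.

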## 2) Objectives

This mixed method study will evaluate whether a multicomponent education strategy improves the ability of Primary Care Providers (PCPs) to identify and triage skin cancer. This study will be deployed in two OHSU family medicine clinics: one OHSU Family medicine rural-based clinic and one urban underserved Federally Qualified Health Center (FQHC) clinic. Baseline data and those not participating in the training will serve as controls.

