## 5) Study Population

### a) Number of Subjects

This study will be conducted at two primary care clinics. Within these two clinics, there are approximately 80 clinicians (e.g. MD, NP, PA, DO, APP).

We will invite all advanced practice providers (MD, NP, PA, DO) at these two clinic sites to participate in the multicomponent educational intervention, up to 40 clinicians per site. These clinicians will take part in the surveys imbedded in the Toolkit, surveys pre-and post-training, and live (in-person/virtual) trainings. Thus, we will recruit approximately 40 clinicians within the 2 clinics for the active intervention.

We will observe the in-person trainings and take detailed fieldnotes. We expect approximately 40 clinicians will participate in each training.

We will interview approximately 5-10 members per site within the clinic.

We will extract EHR data collected from patients from within these two clinics for the year prior and for 1-year post training implementation (2/1/2022-9/30/2024). We estimate up to 200 individuals with biopsies per year, per clinic. For a subset of patients, we will conduct a chart review to affirm use of specific devices to photograph lesions and biopsy results that are not readily ascertainable from EHR data alone.

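### The SAP's referral model pools a rural clinic and an urban FQHC without site or site-by-period terms, so a clinic trend difference can pass as a training effect if uptake also differs by clinic

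*Protocol*

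**What the plan says.** - **Design.** Protocol section 2 places the study in "one OHSU Family medicine rural-based clinic and one urban underserved Federally Qualified Health Center (FQHC) clinic". Section 8 makes the main comparison one of trained clinicians against "clinicians at the same sites that do not have exposure to the multicomponent educational intervention", examined before and after training. Exposure therefore varies between clinicians within each clinic.
- **Uptake.** Section 5a counts roughly 80 clinicians in the two clinics. All are to be invited "to participate in the multicomponent educational intervention, up to 40 clinicians per site", and about 40 are expected across both clinics. Neither document gives the number trained at each clinic.
- **Endpoints.** Section 4 lists among the primary endpoints "total number of referrals to dermatology, number of referrals to dermatology for concerning moles".
- **Protocol model.** Section 8: "Linear mixed-effects regression models adjusting for clustering effects within study sites and other potential confounders will be used".
- **SAP model.** The final approach uses a Poisson GEE with "an exchangeable correlation structure to compare referral outcomes". On its content the SAP says: "The models included exposure to training (Yes/No), pre- and post-training time periods and the interaction of these two indicators as predictors". Site is not on that list. The SAP describes "rates of e-consults, dermatology referrals and biopsies performed (defined as the number of cases per 1000 patients", but for the GEE it states no cluster unit, variance estimator, row unit or offset.
- **Data.** Section 6 and Table 1 of the protocol put a clinician ID and a clinic ID in the analytic data.

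**The concern.** The training-by-period term carries the treatment comparison for the referral endpoints. It is meant to compare the change among trained clinicians with the change among untrained clinicians. With no site terms, both changes are averages over two clinics. If one clinic supplies a larger part of the trained group than of the untrained group, and referrals rise faster at that clinic for reasons of its own, the model credits the difference to training. Nothing in a design that trains by invitation equalises uptake across clinics. A rural clinic and an urban underserved FQHC may also differ in access to dermatology and so in referral trend.

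Clustering on clinician does not remove this. It corrects the standard error, while the problem is bias in the estimate. A spurious ratio tested at a two-sided 5% level could be read as evidence that training changed referral behaviour.

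**Working it through.** The documents give no sample-size calculation, intraclass correlation, referral rate or expected effect, so there is no stated figure to reproduce. The calculations below are illustrative.

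**Inputs from the documents.** Two clinics and about 80 clinicians, about 40 of them trained (section 5a). Yearly patients from the printed totals of Tables 2 and 3: 6251 + 4737 + 6670 + 5012 = 22,670, or 22,670 / 80 ≈ 283 per clinician.

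**Assumed.** 40 clinicians per clinic; trained by clinic 20/20, 30/10 or 35/25; difference in log referral trend between clinics (Δ) of 0, 0.15 or 0.3; referral rate 2% or 4%; clinician log-rate SD 0.6; clinician-by-period SD 0, 0.3 or 0.5.

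**Step 1: size of the bias.** Let pT and pU be the proportions of the trained and untrained groups who work at clinic A, whose log trend exceeds clinic B's by Δ. With no training effect and similar baseline rates, the two groups' average trends differ by

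bias = (pT − pU) × Δ.

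With clinics of equal size and groups of equal size, pT − pU is the difference in trained share between clinics.

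- 20/20: (20/40 − 20/40) × Δ = 0, so no bias whatever the trends.
- 30/10: (30/40 − 10/40) × 0.3 = 0.5 × 0.3 = 0.15; exp(0.15) = 1.16. At Δ = 0.15: 0.075, ratio 1.08.
- 35/25: (35/60 − 5/20) × 0.3 = 0.333 × 0.3 = 0.10; exp(0.10) = 1.11. At Δ = 0.15: 0.05, ratio 1.05.

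**Step 2: false-positive rate.** Null simulation of the exchangeable Poisson GEE on 160 clinician-period rows with a log(patients) offset. There were 54 scenarios of 1500 replicates (Monte Carlo SE about 0.6 points at 5%). The SAP's predictors, clustered on clinician with a robust variance, at nominal 5%:

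| Trained by clinic | Δ = 0.15 | Δ = 0.3 |
|---|---|---|
| 20/20 | 5.0–7.5% (both Δ) | 5.0–7.5% (both Δ) |
| 35/25 | 7.3–9.9% | 9.3–14.9% |
| 30/10 | 7.6–13.2% | 12.7–31.9% |

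With no trend difference the same model gives 5.8–8.7%, so part of the excess over 5% comes from the uncorrected robust variance.

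**Step 3: effect of the site terms.** A site main effect alone changes these rates by at most 0.4 points, because a constant difference in level largely cancels in the pre-post contrast. With site and site-by-period, the mean interaction in the 30/10, Δ = 0.3 case moves from 0.141–0.163 to between −0.010 and 0.021. Over all 54 scenarios the false-positive rate is 6.1–10.5% with the plain robust variance, and 4.5–7.4% with the Mancl-DeRouen variance and a t reference.

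**Step 4: a second set of assumptions.** 30 referrals per 1000, clinician SD 0.5, clinician-by-period SD 0.2, uptake 70% and 30%, 600 runs each.

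- Trend ratio 1.25: (0.7 × 1.25 + 0.3) / (0.3 × 1.25 + 0.7) = 1.175 / 1.075 = 1.09, with 12.8% rejection. After adding the site terms the ratio is 1.00, with 8.3% rejection (robust) or 7.3% (bias-reduced).
- Trend ratio 1.5: spurious ratio 1.17, with 24.2% rejection. After adding the site terms, 1.00, with 6.2% or 4.7%.

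**Step 5: precision cost.** Theory for 30/10: 1/√(1 − 0.5²) = 1.155. The simulated SD of the interaction is unchanged at 20/20, 3–6% larger at 35/25 and 12–16% larger at 30/10.

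**The case against.** **The bias needs two conditions, and the documents show neither.** This stands. Unequal uptake and unequal trends are both required. That one clinic is rural and the other urban shows that they differ, not that their referral trends diverge. The largest figures need a 30/10 split and a 0.3 log difference, about 35% relative divergence. At 35/25 with Δ = 0.15 the rejection rate overlaps the range seen with no trend difference.

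**The protocol's provision for other confounders could cover site.** It could have done so in the planned mixed model. The SAP's predictor list for the final model does not carry it over.

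**This is primarily a feasibility study, as section 4 says.** True, and it limits the weight of any one test. The same section still makes referrals primary endpoints, and both documents set a 5% significance threshold.

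**A tempting stronger reading is that the GEE was clustered on the two sites.** Site is the only clustering level that either document names, and two clusters would give a degenerate sandwich variance. The two cluster scores sum to zero at the solution, so the middle matrix has rank 1 for four coefficients. Simulated false positives are then 39–47% (36.3% under the second set of assumptions). But the reference to sites belongs to the protocol's linear mixed model, and the SAP's GEE text does not mention sites. With exposure defined by clinician and a clinician ID in the data, clustering on clinician is the more natural reading.

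**Nor do the documents show that clustering was ignored.** An exchangeable structure implies some cluster. The unstated cluster unit, variance estimator, row unit and offset are gaps in reporting. They are not evidence of a wrong analysis.

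**Conclusion.** The point holds for the omitted site terms. The SAP's listed predictors leave the referral comparison open to confounding by clinic trend. The size is (pT − pU) × Δ on the log scale: zero at equal uptake, and a spurious rate ratio of 1.16 in the assumed 30/10, Δ = 0.3 case. Confidence is high that the terms are missing from the list. The error rates are illustrative, because the uptake split, trends, referral rate and variance components are all assumed.

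A reader might infer that the completed referral result is wrong. The documents do not support that, since the bias may be nil. The 39–47% figure applies only if clustering on the two sites was carried into the GEE. The point is confined to referral outcomes: the SAP lists e-consult and biopsy rates under descriptive analyses. It should be fixed because the remedy is cheap and the risk cannot be ruled out from what is reported.

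**What to change.** 1. Refit the referral GEE with site and site-by-period added. A site main effect alone is not enough. Use the clinician (study clinician ID) as the cluster, and a robust variance with a small-sample correction, for example Mancl-DeRouen with a t reference.
2. Report the refit beside the SAP's model, labelled as an addition, with the number trained and untrained at each clinic. If uptake was close to equal, the two estimates should nearly agree and the question closes.
3. State in the SAP the cluster unit, variance estimator, row unit and offset actually used. One workable form is a single count per clinician and period, each referral attributed to the clinician on its encounter, with offset log(distinct patients seen by that clinician in the period). Add a rule for patients seen by more than one clinician.

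The cost is a few lines of SAP text and one small refit on identifiers already collected. The loss of precision is nil at 20/20 and largest where uptake is most unequal, which is also where the exposure to bias is greatest.
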